### **Settings:**

The study will be conducted at the Department of Orthodontics, University of Baghdad, as well as in selected private and public dental clinics that provide fixed-appliance orthodontic treatment. All participants will be treated using conventional metal brackets to ensure standardization of the orthodontic appliance type. All procedures, including oral examinations and sample collections, will follow standardized protocols to ensure consistency and uniformity across all study sites.

### **Subjects / Materials:**

#### **Participant Recruitment:**

Participants will consist of patients requiring fixed-appliance orthodontic treatment due to malocclusion, crowding, or spacing issues.

## **Informed Consent:**

Written informed consent will be obtained from all participants prior to enrollment. Participants will receive a clear explanation of the study objectives, procedures, potential benefits, and possible risks. They will be informed that participation is voluntary and that they may withdraw at any time without affecting their ongoing treatment. Confidentiality of participant information will be maintained throughout the study and in all subsequent publications.

## **Inclusion Criteria:**

All included participants will be drawn from those who will receive comprehensive orthodontic treatment and fulfill the following inclusion criteria:

1. Complete permanent dentition up to the first premolar, with no intended extractions in orthodontic treatment plan.
2. Good overall health.
3. Good oral hygiene: full-mouth plaque score < 20%.
4. No bleeding upon probing after 30 seconds.
5. Discontinuous band of plaque at the gingival margin.
6. Normal stimulated salivary flow rate.
7. Normal buffer capacity (final pH between 6.0 and 7.0).

## **Exclusion Criteria:**

1. History of previous orthodontic treatment.

2. Bleaching or topical fluoridation within the last six months.
3. Severely rotated any of the study teeth (limiting the appearance of facial surfaces).
4. Visible signs of caries, fluorosis, hypocalcification, or other developmental defects.
5. Restoration on the labial surface of the study teeth.
6. Systemic or endocrine conditions (e.g., cardiac pacemakers, diabetes mellitus).
7. Craniofacial anomalies and clefts.

### **Sample Size:**

The sample size for the present study was determined to provide 80% statistical power at a 5% significance level ( $\alpha = 0.05$ ) to detect a 1-unit difference in the decalcification index (Gorlick index) (**Hoffman et al, 2014**). Accordingly, the current study will include a total of 75 participants, equally distributed into three groups of 25 subjects each, to ensure adequate statistical power and to account for potential dropouts.

### **Procedure / Intervention:**

- **Group A:** Participants will be instructed to brush their teeth three times daily with the hydroxyapatite-containing toothpaste and to rinse twice daily with a placebo mouthwash.
- **Group B:** Participants will be instructed to brush their teeth three times daily with a conventional fluoride toothpaste and to rinse twice daily with a hydroxyapatite-containing mouthwash.
- **Group C:** Participants will be instructed to brush their teeth three times daily with a conventional fluoride toothpaste and to rinse twice daily with a placebo

mouthwash.

### **Toothbrushing Instructions:**

All participants will receive oral and written instructions, as well as a demonstration video, on proper toothbrushing technique using their assigned toothbrush. The technique applied will be the Modified Bass method, in which the toothbrush is positioned at the gum margin at a 45° angle, performing small vibratory movements while simultaneously moving along the dental arches to ensure that all accessible tooth surfaces are thoroughly cleaned (Farook, 2023).

Each toothbrushing session will be performed for 2minutes, allocating approximately 30 seconds for each quadrant. Participants will be instructed to maintain this routine three times daily throughout the study period.

### **Mouthwash Protocol:**

All participants will be instructed to use the mouthwash according to the following standardized protocol to ensure consistency across the study:

[figure not shown]
- Group A: Placebo mouthwash (purified water, flavoring agents).
- Group B: Hydroxyapatite-containing mouthwash.
- Group C (control group): Placebo mouthwash (purified water, flavoring agents).
  - Frequency of use: twice daily after brushing.
  - Dosage: 15 ml of mouthwash per use.
  - Rinsing duration: Participants will rinse the mouthwash for 30 seconds and then expectorate without swallowing.
  - rinsing instructions: Participants will be instructed not to eat, drink, or rinse with water for at least 30 minutes after using the mouthwash to maximize its

effect.

- Additional Instructions: Participants should shake the bottle well before each use.

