### **Secondary Objectives:**

1. To assess oral health status using Gingival Bleeding Index (GBI), and Plaque

Index (PI).

2. To measure salivary pH changes over the study period.

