### **Blinding:**

This study will be conducted under a double-blind design. Both the principal investigator and the participants will be blinded to group allocation. The toothpaste and mouthwash bottles will be coded and identical in appearance, color, and packaging, ensuring that neither the clinician nor the participant can identify which formulation (hydroxyapatite-containing or conventional) is being used. The code will be kept by an independent researcher who is not involved in the study procedures or data analysis and will only be revealed after the completion of data collection.

All clinical assessments, including Gorelick Index (GI), Diagnodent Pen measurements, digital photography, Gingival Bleeding Index (GBI), Plaque Index (PI), and salivary pH, will be conducted without knowledge of participants' assigned group.

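### The placebo rinse, listed as water and flavouring, is not shown to match the hydroxyapatite mouthwash in look or base, so participant blinding and attribution of B versus C to hydroxyapatite are not secured

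*Protocol*

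**What the plan says.** The Mouthwash Protocol section lists the rinses by group. The control is "Group C (control group): Placebo mouthwash (purified water, flavoring agents", and Group A's rinse carries the same two-item description. The active rinse appears only as "Group B: Hydroxyapatite-containing mouthwash", with no ingredient list, concentration, colour or turbidity. The use instructions are common to all arms: "All participants will be instructed to use the mouthwash according to the following standardized protocol". They include "Participants should shake the bottle well before each use".

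The Blinding section states: "The toothpaste and mouthwash bottles will be coded and identical in appearance, color, and packaging". The stated aim is that "neither the clinician nor the participant can identify which formulation (hydroxyapatite-containing or conventional) is being used". Clinical assessments "will be conducted without knowledge of participants' assigned group".

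Under Procedure / Intervention, Groups B and C use the same type of toothpaste and differ only in the rinse. The secondary objectives cover plaque, gingival bleeding and saliva: "To measure salivary pH changes over the study period".

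**The concern.** The blinding statement describes the bottles. The participant also handles the liquid, at 15 ml twice a day. The listed placebo contains nothing that would reproduce the look of a mineral suspension, and the protocol does not say that it is the active rinse with HAP left out.

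Two things are at stake.

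- **Behaviour.** A participant who guesses which rinse they have may brush, rinse or fill in the diary differently. Plaque and bleeding follow from hygiene, and the Introduction itself links lesion risk to plaque build-up around brackets.
- **Attribution.** Any buffer, surfactant, humectant or preservative present only in the active rinse would be part of the B-versus-C difference. Salivary pH, plaque and bleeding are the outcomes most open to this.

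**Working it through.** The plan gives no figure to reproduce on this point. The check sets the sections side by side.

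**1. What is fixed for each rinse**

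| Feature | Placebo (A and C) | Active (B) |
|---|---|---|
| Ingredients | water and flavouring | HAP; the rest not stated |
| Opacifier or colour match | none listed | not stated |
| Appearance of the liquid | not stated | not stated |
| Bottle | coded, same look | coded, same look |
| Shake instruction | yes | yes |
| Same base as the other rinse | not stated | not stated |

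The bottles are matched on paper. Matching of the liquids is not stated in any row.

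**2. What follows under each possible composition of the active rinse**

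| Active rinse | Look matched by the listed placebo? | B versus C isolates HAP? |
|---|---|---|
| Water, the same flavouring and HAP; particles visible | No | Yes for composition; behaviour remains a route |
| Water, the same flavouring and HAP; clear liquid | Yes | Yes |
| Further base ingredients; particles visible | No | No |
| Further base ingredients; clear and colourless | Possibly | No |

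The plan is sound on both counts in only one of the four rows, and the protocol does not say that this row applies. Visible particles are an assumption: HAP is a sparingly soluble mineral normally carried as particles. The shake instruction is consistent with a product that settles but does not prove it.

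**3. Exposure and contrasts affected**

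- Taking six months as 182 days, each participant takes 2 × 182 = 364 doses of 15 ml.
- Group B has 25 of the 75 participants. The placebo rinse goes to 25 + 25 = 50.
- Of the three pairwise contrasts, A–B and B–C involve different rinses. A–C does not, because both groups use the same placebo.

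**4. Size of the effect**

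The document gives nothing from which to calculate a behavioural or base-ingredient effect, so none is offered.

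**The case against.** The strongest reply is that the Blinding section makes a direct statement of identical appearance, while the look and excipients of the HAP rinse are unknown. The two-item placebo description may be shorthand, and a figure in that section is missing from the text available. That stands: the protocol does not show that the liquids differ.

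A reader might go further and infer that Group B will recognise its product. The documents do not support this. The design is parallel, so each participant uses one rinse; nothing says that participants are told how either rinse looks; and bottle opacity and the dosing vessel are not described. The shake instruction goes to every arm, so it does not mark out Group B and may even help masking.

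A reader might also infer that B versus C is confounded by base ingredients. That too is conditional on a composition not given. The Introduction's remark that rinses help with plaque and gingivitis is weak support, since the cited meta-analysis is, by its title, of an essential-oil rinse with its own agents.

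Safeguards also exist. Assessments are planned blind to group, one trained examiner takes the DIAGNOdent readings, reminders go to all arms, and product checks supplement the diary. These limit bias in measurement and in recorded compliance. They do not stop a participant's own behaviour from changing the plaque, and hence the lesions, that are measured.

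Finally, the aim is worded by product, and a product-level comparison needs no matched base. That is fair, but the Introduction argues from what HAP itself does, so the conclusion has to be limited accordingly if the base is not matched.

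**Conclusion.** The point holds as a gap between the stated blinding and the stated placebo. As listed, the placebo is not shown to match the HAP rinse in appearance or base, and on the assumption of a particle suspension it is unlikely to. Participant blinding is therefore not secured. A B-versus-C difference cannot be attributed to HAP alone unless the active rinse is only water, the same flavouring and HAP.

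Actual recognition by participants and actual confounding by the base are risks, not demonstrated facts. The contrasts exposed are those involving Group B. The magnitude is unknown. This is more than missing detail, because the protocol fixes a specific placebo recipe with nothing in it to support the masking it claims, and analysis cannot repair that after enrolment. It should be corrected, but it does not invalidate the design.

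**What to change.** Before enrolment, reconcile the Blinding and Mouthwash Protocol sections:

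- State the full composition of both rinses.
- Specify the placebo as the HAP rinse's own base without HAP, matched in look with an inert agent.
- Supply both rinses in identical opaque bottles with opaque dosing cups, and say that the liquids, not only the bottles, are matched.

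If a matched base cannot be obtained, keep the opaque containers, withdraw the claim that participants are blinded to the mouthwash, and limit the B-versus-C conclusion to this HAP mouthwash versus flavoured water.

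The first route has a small compounding and packaging cost, which the self-funded study would bear. The fallback costs the containers, some wording and a slightly narrower claim.

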### **Patient Reminder System:**

To enhance adherence to the assigned oral hygiene regimen, all participants will be reminded weekly through one of the social media platforms. These messages will remind the participants in all groups to perform their assigned oral hygiene protocols. The messages will include brief instructions and practical tips for proper use the assigned toothpaste and mouthwash, and participants will be encouraged to confirm completion of their daily oral hygiene routine. This system is designed to improve compliance and ensure standardized adherence throughout the study period.

**Figure 1:** The intended CONSORT Flow Diagram of the Current Study.

CONSORT = Consolidated Standards of Reporting Trials, PP = Per-Protocol Analysis (includes participants who fully adhered to the study protocol), ITT = Intention-to-Treat Analysis (includes all randomized participants, regardless of adherence), T4 = Time point4 (fourth follow-up visit).

## Assessment of WSLs and Oral Health:

White Spot Lesions (WSLs) and oral health parameters will be evaluated at baseline, 1 month, 3 months, and 6 months using DIAGNOdent Pen readings, standardized digital photographs, Gorelick Index, Plaque Index (PI), and Gingival Bleeding Index (GBI). All assessments will follow standardized protocols to ensure consistency across participants.

### Photography and Gorelick Index Assessment

All patients' teeth were photographed using a digital camera. After drying with compressed air, three digital photographs (frontal, right, and left lateral) of each tooth were taken. A single investigator captured all images to ensure consistency in image quality. Photographs were taken at approximately 20° perpendicular to the buccal tooth surfaces (**Papadimitriou et al., 2024**).

The photographs will be evaluated using the Gorelick Index (GI) as follows:

- (0) no white spot lesion present.
- (1) visible white spots without surface interruption (mild decalcification).
- (2) visible white spot lesion having a roughened surface but not requiring a restoration (moderate decalcification).
- (3) visible white spot lesion with surface interruption (severe decalcification).
- (4) cavitation (**Gorelick, Geiger & Gwinnett, 1982**).

### Assessment of White Spot Lesions Using DIAGNOdent Pen:

In this study, the cutoff values of the DIAGNOdent device will be adopted according to the manufacturer's operating guide to standardize data collection in the clinical

setting. Readings from 0–10 represent sound tooth structure, 11–20 indicate outer half enamel caries, 21–30 correspond to inner half enamel caries, and readings of  $\geq 30$  are considered dentin caries (**KaVo Dental, Biberach an der Riss, Germany**). These values will serve as a reference for monitoring changes in white spot lesions during the study (**Du et al., 2011; Gohar, Ibrahim and Safwat, 2023**).

Prior to each measurement, the device will be calibrated for every patient. Readings will be obtained from four locations on the labial/buccal surface of each tooth: gingival, occlusal, mesial, and distal, in accordance with the recommendation of (Banks & Richmond, 1994). After drying the tooth surface, the number 2 pen tip will be placed 1 mm from the bracket on the labial surface of the tooth being examined.

The baseline measurement (T0) will be recorded in the patient's dental chart. Subsequent assessments will be performed at 1, 3, and 6 months (T1, T3, and T6) after the placement of the orthodontic appliance. All measurements will be conducted by a single trained examiner to ensure consistency and reliability.

### **Assessment of Plaque index:**

To determine the Plaque Index (PI) of the patients, the thickness of dental plaque was evaluated by probing the mesial, distal, buccal, and palatal surfaces of all teeth using a Williams periodontal probe. The plaque index for each individual was calculated by summing the scores obtained for each tooth and dividing by the number of teeth examined. The classification of the plaque index was based on **Silness & Löe (1964)**:

- PI 0: No plaque in the area adjacent to the gingiva.

- PI 1: Thin film of plaque along the gingival margin, not visible to the naked eye.
- PI 2: Moderate accumulation of plaque visible on the gingival margin and in the gingival pocket.
- PI 3: Dense accumulation of plaque covering the gingival margin and filling the gingival pocket.

### **Assessment of Gingival Bleeding Index (GBI):**

To evaluate the Gingival Bleeding Index (GBI), gingival bleeding was assessed on the mesial, distal, buccal, and palatal/lingual surfaces of all teeth using a Williams periodontal probe. The probe was gently inserted along the gingival margin and inside the gingival pocket, and bleeding was recorded approximately 30 seconds after probing. The index for each individual was obtained by summing the scores for all teeth and calculating the mean.

The classification of the Gingival Bleeding Index was based on **Löe & Silness (1963)**:

- GBI 0: Healthy gingiva with no bleeding.
- GBI 1: Slight bleeding on probing on one or more surfaces.
- GBI 2: Moderate bleeding observed on multiple surfaces.
- GBI 3: Profuse or spontaneous bleeding involving most or all surfaces.

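### The gingival bleeding grades join an amount of bleeding to a number of surfaces without naming the scoring unit, so some findings have no grade and others meet two; the plaque index formula also needs its divisor clarified

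*Protocol*

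**What the plan says.** The gingival bleeding index and the plaque index are the two measures of oral health status under the Protocol's Secondary Objectives. Both are assessed at baseline and at 1, 3 and 6 months.

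**Bleeding** (Protocol, Assessment of Gingival Bleeding Index). The recording covers four surfaces per tooth: "gingival bleeding was assessed on the mesial, distal, buccal, and palatal/lingual surfaces of all teeth using a Williams periodontal probe". Four grades follow:
- The lowest grade, 0, is for gums that do not bleed at all.
- The first bleeding grade reads "GBI 1: Slight bleeding on probing on one or more surfaces", so it pairs a small amount with any surface count from one upwards.
- The middle grade reads "GBI 2: Moderate bleeding observed on multiple surfaces", so it pairs a larger amount with more than one surface.
- The top grade reads "GBI 3: Profuse or spontaneous bleeding involving most or all surfaces", so it pairs the greatest amount with a majority of the surfaces.

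The participant's value is then formed as follows: "The index for each individual was obtained by summing the scores for all teeth and calculating the mean". The section does not say whether one grade is given per surface or per tooth, or what the mean is divided by.

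**Plaque** (Protocol, Assessment of Plaque index). Four surfaces per tooth are again examined, by "probing the mesial, distal, buccal, and palatal surfaces of all teeth using a Williams periodontal probe", on a scale of 0 to 3. The participant's index comes from "summing the scores obtained for each tooth and dividing by the number of teeth examined". How four surface findings become a tooth's score is not stated.

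**The concern.** A grading scale should give every possible finding exactly one grade. The bleeding scale ties two separate features together, how much a site bleeds and how many surfaces bleed, and defines only some of their combinations. An examiner who finds profuse bleeding on a single surface has no grade to enter. One who finds slight bleeding on two surfaces and moderate bleeding on the other two can justify either grade 1 or grade 2.

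The rule used to resolve such a tooth changes its score, and nothing in the section keeps that rule the same between visits or sites. A statistical analysis plan could not repair this afterwards if only the grade is recorded, because the grade is assigned at the chairside. What is at stake is the precision and interpretability of one secondary outcome. The sample size, which rests on the Gorelick index, is not affected.

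**Working it through.** The Protocol gives no figure to reproduce here, so the check applies its grade definitions literally.

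**1. Grading by surface.** Grade 2 needs several surfaces and grade 3 needs most or all of them. One surface meets neither condition, so only grades 0 and 1 can be used.

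**2. Grading by tooth.** Let each of the four surfaces show no, slight, moderate, or profuse/spontaneous bleeding. That gives 4⁴ = 256 patterns. Let s, m and p be the numbers of surfaces with slight, moderate and profuse bleeding. Read literally:
- grade 0 if s = m = p = 0
- grade 1 if s ≥ 1
- grade 2 if m reaches *multiple*
- grade 3 if p reaches *most*

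The Protocol puts no number on *multiple* or *most*. The main case assumes at least 2 and at least 3.

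*Ungraded patterns in the main case* (s = 0, m ≤ 1, p ≤ 2, some bleeding):
- m = 0: 4 patterns with p = 1, plus 6 with p = 2, total 10
- m = 1: 4 with p = 0, plus 12 with p = 1, plus 12 with p = 2, total 28
- Sum: 10 + 28 = 38

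*Patterns meeting more than one grade in the main case:*
- Grades 1 and 2: 24 with s = 1, m = 2 and a fourth surface either not bleeding or profuse (12 + 12); 6 with s = 2, m = 2; 4 with s = 1, m = 3; total 34
- Grades 1 and 3: 4 with s = 1, p = 3
- Sum: 34 + 4 = 38

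Varying the cut-offs:

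| *Multiple* | *Most* | No grade | More than one grade |
|---|---|---|---|
| ≥ 2 | ≥ 3 | 38 of 256 | 38 of 256 |
| ≥ 3 | ≥ 3 | 62 of 256 | 8 of 256 |
| ≥ 2 | ≥ 2 | 20 of 256 | 74 of 256 |

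Moderate bleeding on one surface only, and profuse bleeding on one surface only, are ungraded in every row. Profuse bleeding on two surfaces is ungraded when *most* means at least three.

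**3. A more lenient reading.** Let the worst amount on the tooth set the grade, and count every bleeding surface towards its extent. In the main case, moderate as the worst amount with one bleeding surface gives 4 ungraded patterns. Profuse as the worst amount gives 4 with one bleeding surface and 6 × (9 − 4) = 30 with two. The total is 38. With *most* at two or more it is 4 + 4 = 8. With *multiple* at three or more it is (4 + 18) + 34 = 56. Overlaps disappear, but the gaps remain.

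**4. Plaque.** With T teeth and score k on every surface:
- Surface scores summed and divided by teeth: 4kT/T = 4k, so the range is 0 to 12. A mouth scoring 1 everywhere gives 4.0, above the scale's top value of 3.
- One score per tooth, as the mean of its surfaces: kT/T = k, range 0 to 3.
- Surface scores summed and divided by surfaces: 4kT/(4T) = k, range 0 to 3.

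The missing step can matter even within the 0–3 readings. For two teeth scored 1, 1, 1, 1 and 2, 1, 1, 0, averaging surfaces gives (1 + 1)/2 = 1.0, while taking the worst surface gives (1 + 2)/2 = 1.5.

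**The case against.** The best defence is that the tooth is the natural scoring unit. The bleeding section sums over teeth, and wording about several or most surfaces makes sense when four surfaces are inspected and one grade given. The unreachable grades at surface level are then no defect. A simple default, under which a finding that misses its surface count drops to the next lower grade, would give all 256 patterns exactly one grade. This is fair as far as it goes: a per-tooth grade is workable. But the default is not in the Protocol, and without it the per-tooth reading has both the gaps and the overlaps shown above.

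The defence is also right about practical weight. Slight bleeding on one or two surfaces is plainly grade 1. Participants must enter without bleeding on probing, so limited bleeding is a plausible early change, but nothing in the Protocol shows that the ungraded combinations will be common. Under Blinding, these assessments are made without knowledge of group, so inconsistent grading should add noise rather than favour an arm.

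Three stronger inferences are tempting and are not supported:
- *That the plaque index is wrongly scored.* The 0–12 range arises only if unaveraged surface scores are summed. One score per tooth fits the 0–3 scale. Even on the 0–12 reading, with four surfaces scored on every tooth, the factor is constant and leaves group tests unchanged.
- *That a quarter of findings cannot be graded.* Counting only teeth on which all bleeding surfaces bleed equally gives 3 of 12 combinations ungraded, or 25%. That count leaves out mixed patterns and depends on the assumed cut-offs. The full count is 38/256 = 14.8%, with a range of 7.8% (20/256) to 24.2% (62/256), and none of these is an expected frequency.
- *That the examiner will have to improvise at every visit.* The Protocol gives no basis for how often ungraded findings will occur.

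**Conclusion.** The point holds for the bleeding index. The stated grades fail when followed: by surface, two of them cannot be reached, and by tooth, they are neither exhaustive nor mutually exclusive under any cut-off tested. The counts rest on four amounts per surface, literal application of the grade definitions, and assumed meanings of *multiple* and *most*. They describe the scale, not how often the problem will arise. The effect is measurement noise of unknown size, blinded to group, in a secondary outcome.

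For the plaque index the conclusion is narrower: an unstated step that needs one sentence, not an error. This is a minor point, worth correcting because it is easy to correct before data collection.

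**What to change.** **Bleeding.** In Assessment of Gingival Bleeding Index, define each grade by amount alone (0 none, 1 slight, 2 moderate, 3 profuse or spontaneous). Score it at each of the four surfaces already probed, and state that the participant's index is the sum of surface scores divided by the number of surfaces examined. Every surface then has exactly one grade, the index runs 0 to 3, and extent enters through the averaging. The percentage of bleeding surfaces can be reported in addition. Using it in place of the graded index would be a matter of choice and would discard the amount of bleeding.

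**Plaque.** In Assessment of Plaque index, state that the summed surface scores are divided by the number of surfaces examined.

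**Cost.** Wording in the Protocol and the case-record form, with room on the form for a score at each surface. No extra probing, staff or visits. The boundaries between slight, moderate and profuse would still rest on the examiner's judgement.
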